## 5.2 Exclusion Criteria

1. Type 1 diabetes mellitus
2. Active chronic liver disease, alcoholic liver disease, Wilson's disease hemochromatosis, primary biliary cirrhosis, primary sclerosing cholangitis, genetic hemochromatosis, known or suspected hepatocellular carcinoma, history of or planned liver transplant for end-stage liver disease of any etiology
3. Documented history of advanced liver fibrosis
4. History of cirrhosis and/or hepatic decompensation including ascites, hepatic encephalopathy, or variceal bleeding
5. Uncontrolled hypertension (systolic > 160 or diastolic > 100 mm Hg)
6. History of acute kidney injury within 12 months of Screening
7. Active infection requiring systemic antiviral or antimicrobial therapy that will not be completed prior to Study Day 1
8. Subjects with a history of major bleed or high-risk of bleeding diathesis
9. Clinically-significant abnormalities in screening laboratory values that would render a subject unsuitable for inclusion, including the following:

- a. Positive test (including trace) for blood on urinalysis. In the event of a positive test, eligibility may be confirmed with urine microscopy showing  $\leq 5$  red blood cells per high power field
  - b. Urine protein/creatinine ratio (UPCR)  $\geq 0.25$  mg/mg. In the event of a UPCR above this threshold, eligibility may be confirmed by a quantitative total urine protein measurement of  $< 300$  mg/24-hr
  - c. Estimated GFR  $< 60$  mL/min/1.73 m^2 (as determined by the Chronic Kidney Disease-Epidemiological Collaboration (CKD-EPI) Equation)
  - d. Alanine aminotransferase (ALT) or aspartate aminotransferase (AST)  $> 2$  x ULN
  - e. Bilirubin  $> ULN$ , unless prior diagnosis and documentation of Gilbert's syndrome in which case total bilirubin must be  $\leq 3$  mg/dL
  - f. Alkaline phosphatase (ALP)  $> 1.5$  x ULN
  - g. Platelet count  $< LLN$
10. Known history of or positive test for human immunodeficiency virus (HIV), hepatitis C or chronic hepatitis B
  11. Uncontrolled hyper- or hypothyroidism. Subjects on dose stable replacement therapy for at least 3 months prior to Screening will be allowed
  12. History of clinically significant acute cardiac event within 6 months before Screening (includes stroke, transient ischemic attack, and coronary heart disease [angina pectoris, myocardial infarction, revascularization procedures])
  13. History of heart failure with NYHA greater than Class II

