All lab samples are to be sent to the central laboratory by overnight courier and processed. Lab Alerts issued as per protocol safety monitoring requirements or stopping rules will indicate the applicable protocol section to facilitate review and will be immediately and simultaneously sent by email to the Investigator, the Sponsor and the CRO Medical Monitors, the Sponsor Drug Safety Physician, and the Clinical Trial Manager (CTM), and should be received by them within 2 days from sample collection. Hematology results from the site's local laboratories are received by the Study Center staff per the local laboratories' standard reporting time and should be entered as soon as possible into the eCRF to inform the Sponsor and CRO study monitoring teams.

All platelet count results must be reviewed promptly (within 48 hours of receipt) by the Investigator, or designee, to ensure that the count has not met the stopping rule and to determine whether the rate of decline is suggestive that the subject could be approaching the dose interruption rule of 75,000/mm^3 as specified in [Section 8.6.3](#). Any case of a platelet count reduction to levels below 50,000/mm^3 is considered an adverse event of special interest and must be reported in an expedited fashion to the Sponsor as per [Sections 9.3.3](#) and [9.4.1](#).

All liver and renal function tests must also be reviewed promptly (within 48 hours of receipt) by the Investigator, or designee, to ensure that the result has not met the stopping rule. Any event meeting renal stopping rules criteria described in [Section 8.6.2](#) is considered an adverse event of special interest and must be reported in an expedited fashion to the Sponsor as per [Sections 9.3.3](#) and [9.4.1](#).

All lab alerts received, including those related to platelet, liver, or renal function monitoring/stopping rules, are also reviewed promptly by the Sponsor and the CRO Medical Monitors who will agree on actions to be taken. Within 24 hours of receiving an actionable lab alert the CRO Medical Monitor will communicate instructions to the Investigator and the study

personnel by emailing them the Safety Surveillance Form that needs to be signed by the Investigator/study personnel and promptly returned to the Sponsor and CRO Medical Monitor. In urgent cases, such as platelet results below 50,000/mm^3, or liver or renal test results reaching a critical stopping rule the Investigator must also be contacted by phone.

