### **8.5.2 Safety Monitoring for Renal Function**

While on treatment all subjects will have renal function tests monitored every 2 weeks during the first 3 months of the study treatment period, and monthly thereafter. Upon completion of the study treatment period, urine renal biomarkers should be monitored as per visit schedule in [Appendix A](#).

In the event of appearance of symptoms or signs consistent with renal dysfunction such as hematuria, polyuria, anuria, flank pain, new-onset hypertension, nausea and/or anorexia, renal function should be tested as soon as possible. Testing at a lab that is local to the subject is permissible for this purpose.

While on treatment during the course of the study, urinary surveillance may include urinalysis to include urine albumin/creatinine ratio (UACR), urine protein/creatinine ratio (UPCR) and urinary red blood cells (RBCs), as well as serum creatinine and cystatin-C, which will be monitored every 2 weeks during the first 3-months of the study treatment period, and monthly thereafter. In addition, other biomarkers of acute renal injury may also be measured if a safety signal is seen that warrants further testing ([Appendix B](#)).

The assessment of serum creatinine, cystatin-C, and urinalysis more frequently than per the Schedule of Procedures in [Appendix A](#), will be guided by consultation with the medical monitor. Any decision taken by the Investigator to discontinue study medication will be made taking into account all available and relevant data. In addition, the decision to discontinue Study Drug may also be based on lesser changes in these parameters observed in isolation or association with other renal-related abnormalities. Any decision taken to restart study medication will be made in consultation with the Study Medical Monitor taking into account all available and relevant data.

All results of renal function tests must be reviewed promptly (within 48 hours of receipt) by the Investigator or the designee to ensure that the result has not met the stopping rules.

Lab alerts for abnormal renal tests will be issued for: Estimated GFR (eGFR) (by CKD-EPI formula) decrease from Baseline > 25%, urine albumin/creatinine ratio (UACR) > 165 mg/g, urine protein/creatinine ratio (UPCR) > 325mg/g, or an increase in serum creatinine from Baseline > 0.3 mg/dL, or new onset hematuria defined as  $\geq 5$  RBC/hpf (except for menstruating females).

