### 8.6.1 Stopping Rules for Liver Chemistry Elevations

In the event of confirmed laboratory results meeting any of the following criteria, dosing of a subject with Study Drug will be stopped permanently:

1. ALT or AST > 8 x ULN, which is confirmed
2. ALT or AST > 5 x ULN, which is confirmed and persists for  $\geq 2$  weeks
3. ALT or AST > 3 x ULN (or the greater of 2 x Baseline value or 3 x ULN if the Baseline value was > ULN), which is confirmed **and** total bilirubin > 2 x ULN or INR > 1.5
4. ALT or AST > 3 x ULN (or the greater of 2 x Baseline value or 3 x ULN if the Baseline value was > ULN), which is confirmed, and the new appearance (i.e., onset coincides with the changes in hepatic enzymes) of fatigue, nausea, vomiting, right upper quadrant

pain or tenderness, fever, rash, or eosinophilia ( $> \text{ULN}$ ) felt by the Investigator to be potentially related to hepatic inflammation/injury

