### **8.6.2 Stopping Rules for Renal Function Test Results**

In the event of an eGFR (by CKD-EPI formula) meeting any of the following criteria, or any change in renal biomarkers deemed by the investigator to require further evaluation, a serum creatinine, urine culture, and urine microscopy sample with inspection of sediment should be immediately obtained.

Dosing of a subject with Study Drug (ISIS 703802 or placebo) will be stopped permanently if testing in any of the following values is confirmed in the absence of an alternative explanation:

1. eGFR (CKD-EPI) decrease of  $> 25\%$  from Baseline
2. eGFR (CKD-EPI) value  $< 45 \text{ mL/min/1.73 m}^2$
3. UACR  $> 165 \text{ mg/g}$
4. UPCR  $> 325 \text{ mg/g}$
5. New onset of hematuria (defined as  $\geq 5 \text{ RBC/hpf}$ )

Irrespective of whether the stopping rule is confirmed or not, the follow-up schedule and frequency of renal function monitoring after the initial event will be determined by the Study Medical Monitor in consultation with the Investigator. The Investigator should consider consulting a local nephrologist for any change of renal function that presents a concern. If a renal biopsy is performed, a sample specimen should be made available for examination by an independent renal pathologist who has been engaged by the Sponsor to review such specimens.

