A confirmed laboratory value is based on consecutive lab values within 7 days (no matter central lab data or local lab data). If consecutive value is the same or worse, then the initial value is confirmed. If the consecutive value is better, then the initial value is confirmed using consecutive value category. In essence, when the consecutive value is better, the initial value is not confirmed. If there is no retest within 7 days then the initial value is presumed confirmed. If there are multiple results on the same day (no matter from the same lab vendor or different lab vendors), then the worst value will be utilized in the analysis.

The following lab results will be graded per Guidance for Industry: Toxicity Grading Scale for Healthy Adult and Adolescent Volunteers Enrolled in Preventive Vaccine Clinical Trials (Sept 2007). The incidence of shift from baseline to worst post-baseline value will be summarized for on-treatment and on-study periods. Post-baseline lab results are defined as any assessment taken after the first dose no matter central lab or local lab data. If a patient is missing a baseline value but has a post-baseline value, then the baseline assessment will be labeled as “unknown”. Likewise, if a patient has a baseline value but has no post-baseline values, then the worst value will be labeled as “unknown”.

- Hemoglobin: shift from baseline to minimum post-baseline value
- WBCs: shift from baseline to minimum post-baseline value
- Platelets: shift from baseline to minimum post-baseline value
- BUN: shift from baseline to maximum post baseline value
- Creatinine: shift from baseline to maximum post-baseline value
- eGFR: shift from baseline to minimum post-baseline value
- Proteinuria: shift from baseline to worst post-baseline value
- ALT: shift from baseline to maximum post-baseline value
- AST: shift from baseline to maximum post-baseline value
- Alkaline phosphatase: shift from baseline to maximum post-baseline value
- Total bilirubin: shift from baseline to maximum post-baseline value

eGFR by will be graded using the following criteria:

- ≥ 90 mL/min/1.73m²
- ≥ 60 mL/min/1.73m² to < 90 mL/min/1.73m²
- ≥ 30 mL/min/1.73m² to < 60 mL/min/1.73m²
- ≥ 15 mL/min/1.73m² to < 30 mL/min/1.73m²
- < 15 mL/min/1.73m²

Shift tables for eGFR, ALT, AST and total bilirubin will be provided using confirmed values as well.

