The number and percent of patients who met a protocol-defined safety monitoring rule(s) and stopping rule(s) (see Protocol Section 8.6 for details) will be tabulated by treatment group. A listing

will be provided for patients who met protocol-defined safety monitoring rules and for patients who terminated treatment due to a protocol-defined stopping rule as well.

Additional investigation of hepatobiliary laboratory assessments, platelet counts and renal parameters will be performed for on-treatment and on-study periods as below.

Hepatobiliary Laboratory abnormalities: The number and percent of patients falling in each of the following category will be tabulated by treatment group:

- The higher of ALT > 3 x upper limit of normality (ULN) or ALT > 2 x baseline
- ALT/AST > 3 x ULN
- ALT/AST > 5 x ULN
- ALT/AST > 8 x ULN
- ALT > 3 x ULN - ≤ 5 x ULN
- ALT > 5 x ULN - ≤ 8 x ULN
- Total bilirubin > 2 x ULN
- ALP > 2 x ULN and (baseline ALP < 2 x ULN or baseline ALP missing)

The number and percent of patients falling in each of the following categories based on confirmed worst post-baseline assessments will be tabulated by treatment group and for pooled ISIS 703802.

- ALT/AST > 8 x ULN, which is confirmed
- ALT/AST > 5 x ULN, which is confirmed and persist for at least 2 weeks
- ALT/AST > 3 x ULN (or the greater of 2 x Baseline value or 3 x ULN if the Baseline value was > ULN), which is confirmed and either:
 - Total bilirubin > 2 x ULN, or
 - INR > 1.5, or
 - Temporal association with symptoms of fatigue, nausea, vomiting, right upper quadrant pain or tenderness (coded as abdominal pain or abdominal pain upper),, fever, rash or eosinophilia as a reported laboratory result > ULN; and where temporal will be defined as the report date of the confirmed laboratory parameter occurring within the interval of the associated adverse event start and stop dates.

For patients having confirmed 3-fold or greater elevations above the ULN for ALT or AST, a listing of all the ALT, AST, total bilirubin, INR, and alkaline phosphatase records will be provided.

Abnormalities of platelet counts: The number and percentage of patients falling in each of the following categories (using available central and local laboratory assessments) based on post-baseline assessments will be provided:

- Any 2 occurrences of platelet count < 140,000/mm³
- Any single occurrence of platelet count < 100,000/mm³

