- Any 2 occurrences of platelet count < 140,000/mm³ and any single occurrence of platelet count < 100,000/mm³

The nadir platelet count will be summarized by below categories:

- Decrease \geq 30% of baseline
- Decrease \geq 50% of baseline
- 100,000/mm³ to < 140,000/mm³
- 75,000/mm³ to < 100,000/mm³
- 50,000/mm³ to < 75,000/mm³
- 25,000/mm³ to < 50,000/mm³
- 0 to < 25,000/mm³

All categories of abnormalities in platelet count will be provided using confirmed values for on-study period as well.

Abnormalities of renal function: The number and percentage of patients falling in each of the following categories based on confirmed worst post-baseline assessments will be provided:

- eGFR by CKD-EPI > 25% decrease from baseline
- eGFR (CKD-EPI) value < 45 mL/min/1.73 m²
- urine albumin/creatinine ratio (UACR) > 165 mg/g (0.165 mg/mg)
- urine protein/creatinine ratio (UPCR) > 325 mg/g
- New onset hematuria defined as \geq 5 RBC/hpf (except for menstruating females)

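### Entry criteria set no UACR limit and no ceiling on spot UPCR after the 24-hour override, so a subject may enter already above an absolute renal stopping limit

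*Protocol*

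**What the plan says.** **Entry.** Items 9a to 9g of Protocol Section 5.2, repeated in the synopsis, contain no UACR criterion. Item 9b excludes a spot UPCR of 0.25 mg/mg or more and then allows an override: "In the event of a UPCR above this threshold, eligibility may be confirmed by a quantitative total urine protein measurement of" less than 300 mg per 24 hours. No upper bound on the spot value accompanies the override. Both ratios are measured at Screening (Appendix A, extended urinalysis and its footnote e).

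**Stopping.** Under Section 8.6.2, dosing "will be stopped permanently if testing in any of the following values is confirmed in the absence of an alternative explanation". The list includes UACR above 165 mg/g and UPCR above 325 mg/g, both absolute. In the same list the 25% eGFR fall is measured from Baseline, and hematuria counts only if new. Section 8.5.2 uses the same two ratios as alert levels.

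**Reporting.** Section 6.2 opens its rule with "Any event meeting renal stopping rules criteria described in" Section 8.6.2, and makes such an event an adverse event of special interest with expedited reporting.

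**Analysis.** SAP Section 3.5.2 specifies: "Abnormalities of renal function: The number and percentage of patients falling in each of the following categories based on confirmed worst post-baseline assessments". The UACR and UPCR categories have no baseline condition. In the same section the ALP category does: "ALP > 2 x ULN and (baseline ALP < 2 x ULN or baseline ALP missing"). The SAP also states: "If there is no retest within 7 days then the initial value is presumed confirmed".

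**The concern.** A stopping rule should respond to change on treatment. If a value that was acceptable at entry already exceeds an absolute stopping limit, the rule can fire on a subject in whom nothing has happened.

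For such a subject the consequences follow in sequence. The first on-treatment sample raises a lab alert. Section 8.5 then withholds dosing until the Study Medical Monitor has reviewed a confirmatory test. If the value is confirmed and no other explanation is accepted, dosing ends permanently and the event is reported as one of special interest. Section 9.4, by contrast, says a pre-existing condition that has not worsened is not recorded as an AE. In the SAP the confirmed value is counted as a post-baseline renal abnormality.

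Renal safety is a real question for this compound. Section 2.3.3.2 describes kidney changes with proteinuria as the most noteworthy monkey finding, and Section 2.5.2 names the kidney as an organ of high distribution. Counts that reflect entry status rather than drug effect make that signal harder to read.

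**Working it through.** The documents give no figure of their own on this point. The check compares entry and stopping limits on one scale.

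**1. Units.** 0.25 mg/mg × 1000 = 250 mg/g.

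**2. UPCR, standard route.** Entry below 250 mg/g, stop above 325 mg/g; 325/250 = 1.3. No overlap.

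**3. UPCR after the override.** The spot value has no ceiling, so one above 325 mg/g is admissible. Spot and 24-hour results need not disagree for this. With average UPCR = 24-hour protein ÷ 24-hour creatinine and protein at 299 mg, UPCR exceeds 325 mg/g when creatinine is below 299/0.325 = 920 mg/24 h. Creatinine excretion is not in the documents; over an assumed range:

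| Creatinine (g/24 h) | UPCR at 299 mg protein (mg/g) |
|---|---|
| 0.8 | 299/0.8 = 374 |
| 1.0 | 299/1.0 = 299 |
| 1.2 | 299/1.2 = 249 |
| 1.5 | 299/1.5 = 199 |

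Above 920 mg/24 h, the spot value must exceed the 24-hour average for the overlap to occur.

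**4. UACR.** Albumin is part of urine protein, so in one sample the albumin share needed for UACR above 165 mg/g is 165 ÷ UPCR.

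| UPCR (mg/g) | Route | Albumin share needed |
|---|---|---|
| 165 or less | standard | not possible |
| 200 | standard | 165/200 = 82.5% |
| 249 | standard | 165/249 = 66.3% |
| 250 | override | 165/250 = 66.0% |
| 325 | override | 165/325 = 50.8% |

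The UACR overlap therefore does not depend on the override, though without it the window is UPCR between 165 and 250 mg/g with mostly albumin.

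**5. Other rules in the protocol.**

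| Test | Entry | Permanent stop | Protection for pre-existing values |
|---|---|---|---|
| ALT/AST | ≤ 2 × ULN | > 8 × ULN; > 5 × ULN for ≥ 2 weeks; > 3 × ULN only with bilirubin > 2 × ULN, INR > 1.5, or new symptoms or eosinophilia | Gap, plus Baseline clause in the combined rules |
| eGFR | ≥ 60 | < 45, or fall > 25% | Gap of 1 − 45/60 = 25% |
| Platelets | ≥ LLN | < 50,000/mm³, or < 75,000/mm³ on a reduced dose | Gap |
| Hematuria | Section 5.2, 9a | ≥ 5 RBC/hpf | Must be new |
| UPCR, override | no ceiling | > 325 mg/g | None |
| UACR | no limit | > 165 mg/g | None |

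The ALT/AST Baseline clause reads "or the greater of 2 x Baseline value or 3 x ULN if the Baseline value was" above ULN. With Baseline at the entry limit of 2 × ULN, the combined-rule threshold is the greater of 2 × 2 = 4 and 3, that is 4 × ULN, or twice the entry limit.

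**6. Weight of one case.** With about 24 subjects per group, one subject is 1/24 = 4.2 percentage points in the renal table.

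**The case against.** The strongest reply is that judgement fills the gap. Criterion 9 has an open-ended stem and criterion 30 lets the Investigator or Sponsor exclude anyone unsuitable. The stop yields to an alternative explanation, for which a documented pre-treatment value is an obvious candidate. Section 8.5.2 adds Medical Monitor review and says: "Any decision taken by the Investigator to discontinue study medication will be made taking into account all available and relevant data". Section 9.5.1 keeps abnormalities judged not clinically significant out of AE reporting. All of this stands and will catch some cases. None of it says how a pre-existing UACR or UPCR is to be treated, so sites may differ. The 24-hour collection that clears a spot UPCR at entry is also not among the supplemental tests listed in Sections 8.5.2 and 8.6.2; it could be done only as an optional additional study.

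Second, the SAP is not blind to baseline. Section 3.5.2 also gives a proteinuria shift from baseline, change and percent change for quantitative urinalysis, and full listings, all alongside placebo. A reader might infer that pre-existing values would be invisible; these displays show otherwise. They do not correct the category table, and UACR is not in the shift list.

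Third, a reader might infer that every other rule is free of this problem, or that the liver rule leaves only a 1.5-fold margin (3/2). Neither is right. ALT/AST above 3 × ULN alone never stops dosing. The protocol also admits subjects with Gilbert's syndrome and bilirubin up to 3 mg/dL while alerting on any bilirubin above ULN, so entry above an alert level is tolerated there. Bilirubin alone is not a stop, however, whereas UACR and UPCR are.

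Finally, one could say a clarifying sentence in 8.6.2 would do more than an entry limit. If it exempted pre-existing values, it would also let subjects continue dosing above the sponsor's own renal limit.

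**Conclusion.** The gap holds as a cheap improvement. The text allows entry above the UACR or UPCR stopping limit, and an unchanged value can then cause a hold and possibly a permanent stop. That such a subject must be stopped does not follow, because the stop requires confirmation and the lack of another explanation.

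The size is unknown: the documents give no distribution of UACR, UPCR or creatinine excretion. The overlap needs a largely albumin proteinuria on the UACR route, and low creatinine excretion or discordant results on the UPCR route. The UACR shares assume both ratios come from the same sample.

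A reader might infer damage to the efficacy comparison or an imbalance between groups. The documents do not support either. The SAP's FAS keeps the subject, with multiple imputation if the primary endpoint is missing. Failing the dose requirement of the SAP's PPS takes a stop before 22 weekly or 5 monthly doses. Randomization gives no reason to expect such subjects to favor one group, though in groups of 24 chance alone could place one or two unevenly.

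**What to change.** Three edits:

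1. In criterion 9 of Section 5.2 and the synopsis, add the exclusion: *UACR > 165 mg/g at Screening (retest allowed per 6.1.1)*.
2. End item 9b with: *provided the spot UPCR is ≤ 0.325 mg/mg*.
3. In SAP Section 3.5.2, count UACR > 165 mg/g and UPCR > 325 mg/g as post-baseline abnormalities only when the baseline value is at or below the limit or missing, following the ALP category. List subjects above the limit at baseline separately.

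Leave the 8.6.2 limits unchanged, so that no safety limit is relaxed.

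Edits 1 and 2 need no new test. They cost slightly narrower eligibility, a few more screen failures and part of the 24-hour override. They reach only subjects not yet enrolled; edit 3 also covers those already in the trial. Little headroom remains just below the limits: a subject at UACR 160 mg/g crosses on a 3.1% rise (165/160 − 1), and one at UPCR 320 mg/g on a 1.6% rise (325/320 − 1). The SAP's separate tabulation of subjects meeting protocol stopping rules is not altered by edit 3 and should be read with the new listing.
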